6.7 Collection and/or destruction of medicines

It is the sponsor's responsibility to ensure the destruction of any partially used or unused Experimental Product. A detailed form describing the returned Experimental Product will be developed with the Investigator, and will be signed by the Investigator and the Monitoring Team.

6.8 Accounting and adherence to treatment

Each dose of study treatment will be administered by a study pharmacist, with the patient being monitored for 30 minutes after administration. If the patient vomits or rejects treatment during the 30 minutes, the same dose will be administered again. The study pharmacist should record the information on the appropriate CRF page. Next, the monitor responsible for the study will check the data in the CRF by comparing it with the Experimental Product he/she has collected and the treatment registration forms. All measures will be taken to ensure that patients receive treatment in accordance with the protocol.

7. MEASURES TO MINIMIZE BIAS: RANDOMIZATION AND BLINDING

An electronically generated randomization list was prepared by an independent statistician, with 110 blocks of 4 participants per block. This randomization list was generated on R software (Package 'blockrand'). The list will be accessible only to non-blinded pharmacists in the study, in an attempt to minimize observation bias. Participants will be randomized by the study pharmacist to their designated treatment regimen at the time of inclusion and will be subsequently identified throughout the study only by their allocated study number, always assigned following chronological order. In case of SAEs, unmasking will be available to DSMB members, and preliminary analyses will be performed even before the scheduled interim analyses, in order to guide early halting of any of the CQ arms. The randomization and blinding procedure will be described in a specific SOP.

7.1 Compliance with the study intervention

Each dose of the study product will be administered by a qualified and licensed member to administer the study product. Administration date and time will be inserted in the case report form (CRF).

7.2 Concomitant therapy

All concomitant therapies will have a medical indication, and will be registered in CRF, for later analysis.

7.3 Salvage drug

N/A

8. DISCONTINUATION OF THE INTERVENTION AND WITHDRAWAL OF THE STUDY

8.1 Criteria for stopping and discontinuing study intervention

8.1.1 Interruption of administration

The study drug will be maintained for 10 days according to the indicated group, regardless of their hospitalization for the same or longer period. Patients who are discharged before then will be contacted on the evaluation days provided for in the protocol.

8.1.2 Interruption of study for safety reasons

Given the severity of COVID-19 disease, there are no pre-specified stopping rules. Thus, there will be careful supervision by the protocol team and security monitoring committee, and frequent analyses, in real time.

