1.11 Study duration

The study will last for the period of appearance of cases (expected between April 6th and August 31st, 2020), or until the sample is completed, or until the interim analysis shows a clear benefit or harm. The period was calculated based on our modeling of the number of cases in Manaus, as shown below.

To obtain a possible scenario of infected by COVID-19 in the city of Manaus, we used simulation using the SIR model (Susceptible, Infected and Recovered) to have an idea of the probable period when we will have the peak of infection in the city of Manaus. The parameters used for the modeling were as follows: R0 = 2.5, from studies in China; the Susceptible rate 0.92, the infected rate 0.01 and the Recovered rate 1/14. The first case found in Manaus was diagnosed on March 11^{th} , 2020.

The obtained result can be seen in the graph below.

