1.11.2 Safety

Given the severity of the disease COVID-19, there is no study pre-specifying criteria for interrupting follow-up. The protocol team will review blind AE/SAE data every 2 weeks. If there is a worrying number of unexpected AEs, the researcher will request a review of the non-hidden security data in an ad hoc meeting with the external security monitoring committee, which should take place in real time, via videoconference.

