10.2 Sample calculation and interim analysis

The sample for the primary outcome (reduction in lethality in patients with severe respiratory virus treated with a high dosage of chloroquine compared to a low dosage) was calculated based on the following assumptions:

- 3. The 20% lethality incidence in critically ill patients per year in the low dosage group;
- 4. High dosage chloroquine will be able to reduce lethality by at least 50% compared to low dosage chloroquine;

Thus, considering a test of differences in proportions between 2 groups of the same size, with power of 80% and alpha of 5%, 394 participants will be needed (197 per group). Considering 10% losses, the sample size is 440 participants.

To include interim analyses, we recalculate the sample sizes required in each of the analyzes and in the final analysis, using an alpha-spending function approach, in which the type 1 error is controlled by alpha correction final, based on the alphas used for interim analyses. There are several alpha spending functions and there is always a trade-off between how much will be 'spent' on the interim analysis and the final sample size required. In summary, the more difficult it is to reject the null hypothesis in the interim analysis, the less alpha will be spent and the impact will not be large. We will use Hwang-Shih-DeCani spending functions with $\gamma = -4$ for the upper limit (that is, to interrupt the study that rejects the null hypothesis in the interim analysis), which corresponds to a conservative method, equivalent to the upper limit of O 'Brien-Fleming, with little impact on the final sample size. We will also include a lower limit for testing futility, also using the Hwang-Shih-DeCani spending function, but with a less stringent $\gamma = -2$ parameter for a beta spending function. Although the calculation includes a possible interruption due to futility, this can be ignored, at the discretion of the DSMB (or equivalent) without any impact on the type 1 error.

The table below shows the calculations for the 3 interim analyses and for the final analysis, showing both the sample size required in each analysis as well as the upper (one-tailed 2.5%) and lower limits.

| | | | Superior Limit | | | |
|------------|---|----|----------------|--------|-----|--------------|
| Sample | | | | | | |
| size | | | | p one- | | |
| percentage | | N | Z | tailed | Z | p one-tailed |
| | | 10 | - | 0.278 | 3.1 | |
| 25% | 8 | | 0.59 7 | 6 | | 0.0008 |

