| | | 21 | 0.3 | 0.638 | 2.8 | |
| 50% | 5 | 5 | 6 | 2 | | 0.0024 |
| | | 32 | 1.1 | 0.882 | 2.4 | |
| 75% | 2 | 9 | 1 | 4 | | 0.0074 |
| | | 42 | 2.0 | 0.978 | 2.0 | |
| 100% | 9 | 1 | 0 | 1 | | 0.0220 |

The procedure will be based on the calculation of the Z value of the difference of proportions test in each of the analyses, and the study will continue if this value is between the values of the lower and upper limits and will be interrupted if it is above the upper limit (by rejection H0) or below the lower limit (for futility), remembering that the latter can be ignored without prejudice to the calculations.

All calculations in this report were made in the R environment, version 3.6.1, with the functions implemented in the TrialSize and gsDesign packages. Other intermediary analyzes can be carried out throughout the study to periodically monitor the safety of participants and will provide possible prior information on treatment to the DSMB and Ministry of Health.

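### The protocol promises to stop for clear harm but states that it has no safety stopping rule, and its only lower limit is an ignorable futility bound that cannot identify harm

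*Protocol*

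**What the plan says.** - Section 1.11 (Study duration): recruitment runs for the epidemic period, to full sample, or "until the interim analysis shows a clear benefit or harm".
- Section 8.1.2: under a heading on interruption for safety, "there are no pre-specified stopping rules". Supervision and frequent analyses are offered instead.
- Section 1.11.2: "there is no study pre-specifying criteria for interrupting follow-up". AE and SAE data are reviewed blinded every two weeks. The trigger for an unblinded committee meeting is "If there is a worrying number of unexpected AEs", with no number attached.
- Section 7: after SAEs the DSMB can unmask, and "preliminary analyses will be performed even before the scheduled interim analyses, in order to guide early halting of any of the CQ arms". No threshold is given.
- Section 10.2: an upper limit rejects the null hypothesis (Hwang-Shih-DeCani, gamma = -4, one-tailed 2.5%). "We will also include a lower limit for testing futility", with beta spending at gamma = -2. The study is to be interrupted above the upper limit or below the lower one, "remembering that the latter can be ignored without prejudice to the calculations".
- Sections 8.1.6, 11.3 and 11.9 add general grounds for stopping (risk-benefit doubt, unacceptable risk, interim results) and an independent committee that recommends whether to continue.

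The sign of Z is not defined. The primary objective (1.4.1) and the effect assumption in 10.2 imply that a positive Z means fewer deaths on the high dose.

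**The concern.** The protocol names clear harm as a reason to end the trial, then says that no criterion for it exists. Its numerical limits address benefit and futility only.

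This matters because the arms differ greatly in exposure. From section 6.2, group 1 receives 1,200 mg × 10 = 12,000 mg and group 2 receives 900 + 4 × 450 = 2,700 mg. Section 2.3.1.1 lists arrhythmia and cardiac arrest among the drug's toxicities, and the primary endpoint is death. Excess mortality on the higher dose is a plausible result, and the committee would meet it at an interim look with no agreed standard for reading it.

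The route to unblinded review in 1.11.2 depends on unexpected AEs, while section 9.6 says that efficacy outcomes are, a priori, not counted as AEs unless the investigator finds them exceptional. A simple excess of deaths may therefore not pull that trigger.

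**Working it through.** **1. Reproducing the plan's design.** Inputs from 10.2: 20% against 10% mortality, 80% power, 5% two-sided alpha.

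- Fixed design, unpooled variance: n = (1.96 + 0.8416)² × (0.20×0.80 + 0.10×0.90) / 0.10² = 196.2, so 197 per arm and 394 in total, as stated. 394/0.9 = 438, against the stated 440.
- Spending: α(t) = α(1 − e^(−γt))/(1 − e^(−γ)). With γ = -4 and α = 0.025, the first look spends 0.0008, so Z = 3.155. Numerical recursion over four equal looks gives upper Z = 3.155/2.818/2.439/2.014 (p 0.0008/0.0024/0.0074/0.0220, as tabulated).
- Lower limit (beta 0.20, γ = -2, non-binding): Z = -0.587/0.355/1.185/2.014, maximum N about 428 against 429. These agree with the table as far as its broken digits can be reassembled.
- Type I error with the lower limit ignored is about 0.025, so the protocol is right that ignoring it does no damage to efficacy alpha.

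**2. What the lower limit detects.** Z = (p_low − p_high)/√[p̄(1 − p̄)·2/n]. With 20% observed on the low dose, the limit is reached at these high-dose rates:

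- Look 1 (n = 54 per arm): about 24.7%. Check: -0.047/√(0.2235×0.7765×2/54) = -0.59.
- Look 2 (n about 107): about 18.1%.
- Look 3 (n = 161): about 15%.

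At looks 2 and 3 it is therefore crossed even when the high dose has somewhat fewer deaths.

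**3. Chance of having crossed the lower limit** (simulated pooled Z, low dose 20%; the 30% and 40% rates are assumptions, not protocol values):

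| True high-dose mortality | Look 1 | By look 2 | By look 3 |
|---|---|---|---|
| 20% (equal) | 27% | 67% | 89% |
| 30% | 74% | 98% | >99% |
| 40% | 96% | 100% | 100% |

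Crossing by look 2 is the usual result under no effect as well as under harm.

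**4. An example harm bound.** One-sided 2.5%, γ = 1: the first look spends 0.025 × (1 − e^(−0.25))/(1 − e^(−1)) = 0.0087, so Z = -2.376. The four limits are -2.376/-2.357/-2.350/-2.357. Chance of having crossed:

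| True high-dose mortality | 25% | 50% | 75% | 100% |
|---|---|---|---|---|
| 30% | 12% | 29% | 44% | 58% |
| 40% | 48% | 83% | 96% | 99% |

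At equal doses the total is about 2.5%.

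**5. Excess deaths.** Continuing from 108 to 429 patients would mean (429 − 108)/2 × 0.10 = 16 excess deaths at 30% against 20%, and × 0.20 = 32 at 40% against 20%. On average the example bound averts about 4.5 of the 16 and about 24 of the 32. The existing futility bound, if followed, averts about 14.5 and 31.6.

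Steps 3 to 5 assume that day-28 outcomes are known for everyone counted at each look. The schedule (1.12, note b) times the reviews by participants included, so real information would be less.

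**The case against.** The best defence is that the plan stops for harm by committee judgement, and that this is legitimate. The DSMB can unmask and analyse early (section 7), further safety analyses are allowed (10.2), general grounds for stopping are listed (8.1.6, 11.3), and an independent committee advises on continuing (11.9). Section 8.1.2 is headed as a safety section, so it need not contradict the efficacy and futility limits in 10.2. Falling below the lower limit is a default stop, and any observed excess of high-dose deaths at looks 2 or 3 falls below it. A numerical harm bound is partly a design preference, and a DSMB charter may hold one.

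Most of this stands, and it rules out three stronger readings.

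- A reader might infer that no level of excess mortality calls for a recommendation. That is not so: the futility default would usually stop a harmful trial, and the DSMB has wide discretion.
- A reader might infer that harm can never be shown with error control. Section 10.1 tests at p<0.05, so a final comparison in the harm direction is available. The gap is at the interim looks.
- A reader might take the 16 or 32 excess deaths as preventable by a harm bound. They arise only if a crossed futility bound is overridden, and the example bound averts only part of them.

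The defence does not remove the conflict between 1.11, which promises a stop for clear harm, and 1.11.2 and 8.1.2, which state that no criterion exists. The point rests on those statements, not on silence that a charter could fill.

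**Conclusion.** The concern holds in a limited form. The protocol promises to stop for clear harm, states that it has no pre-specified safety criterion, and offers as its only lower limit a non-binding futility bound. By look 2 that bound has been crossed in about 67% of trials with equal doses and about 98% at 30% against 20%, so a crossing cannot be read as harm. Stopping for harm rests on DSMB judgement, with no harm-specific or error-controlled interim criterion. Following the futility bound would usually protect patients, but a committee that chooses to set it aside has nothing further to consult.

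The size rests on 20% low-dose mortality (the protocol's assumption), on 30% and 40% as illustrative high-dose rates, on complete day-28 data at each look, and on the inferred sign of Z.

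**What to change.** 1. Reconcile sections 1.11, 1.11.2, 7, 8.1.2 and 10.2. Delete the sentence in 8.1.2 that denies any stopping rules, or limit it to what it is meant to cover.
2. Add to 10.2 a statistical harm guideline for the DSMB on day-28 mortality at each scheduled look, distinct from futility and spent separately from efficacy alpha. One-sided 2.5% with Hwang-Shih-DeCani gamma = 1 (Z about -2.36) is one example; the DSMB and sponsor choose the function. Define the sign of Z in the table.
3. State its operating characteristics under assumed rates: crossed by 50%/75% information in about 29%/44% of trials at 30% against 20% and 83%/96% at 40% against 20%, and about 2.5% in total at equal doses. Its limits should be reported too: at 30% against 20%, about 42% of trials never cross it.
4. Say that the 2.5% covers scheduled looks only. Looks triggered by observed SAEs depend on the data, so recomputing the bound from the spending function does not guarantee the error rate there.

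The cost is one column in the boundary table, an entry in the DSMB charter, and a chance of about 2.5% of crossing the harm bound at scheduled looks when the doses are equal. No efficacy alpha is spent.

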8.1.3 Withdrawal from randomized treatment or study

Patients may withdraw from the study at any time, upon request, without any consequences. Patients should be listed as having their consent withdrawn only when they no longer wish to participate in the study and no longer authorize investigators to make efforts to continue obtaining information.

Efforts must be made to maintain patients entering and participating in the study. Patients should be told about the scientific importance of their data, even if they discontinue treatment with the study drug.

8.1.4 Study drug discontinuation

The patient can stop taking the study drug for any of the following reasons;

- 1. Patient requests to discontinue study medication;
- 2. The occurrence of any medical condition or circumstance that exposes the patient to substantial risk:

3. Any serious adverse event (SAE), clinically significant adverse event, serious laboratory complications, abnormality, intercurrent illness or other medical condition that suggests to the investigator that participation is not safe;

The reason for the patient discontinuing use of the study drug should be documented on the case report form

8.1.5 Withdrawal of patients from the study

A patient can be withdrawn from the study after initial administration for the following reasons:

- 1. The patient withdraws consent or requests to discontinue the study for any reason;
- 2. Death of the patient;
- 3. Study closure.

Patients who withdrew from this study after signing the consent and administration of the study product, will not be replaced. The reason for discontinuing the study patient will be recorded on the case report form.

8.1.6 Study interruption

- 1. If information about the product raises doubts about the risk-benefit ratio;
- 2. If the results of the clinical study do not appear to be scientifically convincing;
- 3. If there is no longer any interest in the clinical study arm or in the case of its obsolescence;
- 4. In case of non-compliance, by the researcher, with a fundamental obligation, including, among others, the violation of the clinical study protocol, the non-compliance with applicable laws and regulations or non-compliance with the ICH standards related to Good Clinical Practices;
- 5. If the treatment is instituted as standard treatment by the Ministry of Health or another reliable scientific society, national or international.

9. STUDY EVALUATIONS AND PROCEDURES

9.1 Definition of source documents

All data and information requested in the clinical record form (CRF) will be collected in the electronic medical record of the patients or in interviews with the patient or his caregiver, including vital and clinical signs, concomitant diseases and any possible concomitant medications. Demographic data will be recorded in the center file or in the patient's medical file (MedView electronic medical record system), together with the viremia results for COVID-19. Clinical information and the results of laboratory tests will be obtained from the electronic hospital record and inputed by the team on tablets, which will have an online connection with REDCap, where the information will be stored in real time, using the FMT-HVD server.

9.2 Security instructions

The safety and tolerability of treatments will be assessed based on the registration of Adverse Events (AEs) and the classification of laboratory assessments and vital signs. A severity rating scale, based on the toxicity rating scales developed by the WHO and the National Institutes of Health, Division of Microbiology and Infectious Diseases, will be used to rate the severity of all symptoms, physical examination findings and results of hemoglobin. All laboratory abnormalities - with Grade 2 or greater for biological data - with clinically significant abnormalities (regardless of degree) must be monitored until resolution or until their progression stabilizes.

Virology exams will be carried out at LACEN - AM, linked to the Health Surveillance Foundation, in partnership with the Leônidas & Maria Deane Institute. The coronavirus diagnostic protocols will follow the routine recommended by the Ministry of Health, with RT-PCR.

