1.4.2 Secondary outcomes

- 1. Mortality on days 7 and 14;
- 2. Clinical status of the study subject on days 14 and 28;
- 3. Daily clinical status during hospitalization;
- 4. Time on supplemental oxygen (if applicable);
- 5. Time on mechanical ventilation (if applicable);
- 6. Length of hospitalization;
- 7. Data and cause of death (if applicable);
- 8. Incidence of adverse events;

9. Incidence of serious adverse events (grades 3 and 4).

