- # Participant may be hospitalized or discharged. In the latter case, there will be no outpatient return visit and the main outcome will be assessed by telephone. Note: all procedures will be performed during the hospitalization period and will be interrupted if the participant is discharged;
- a Inclusion/exclusion criteria will be fully assessed at visit D1, prior to inclusion. The diagnosis of SARS-CoV2 will occur a posteriori.
- b Randomization will take place in blocks of 4 with 110 participants each. There will be interim reviews when 25%, 50% and 75% of participants are included;
- c A complete medical history will be obtained prior to randomization to include assessments of cardiovascular, metabolic (for example, Type I or II diabetes mellitus), psychiatric (such as depression), renal (such as nephrolithiasis, nephropathy, renal failure) and bone disorders;
- d Physical examination will consist of evaluation of vital signs (heart rate, respiratory rate, systolic, diastolic and mean blood pressure, peripheral oxygen saturation) and signs and symptoms present;
- e Assessments to highlight any visual and/or mental alterations resulting from chloroquine;
- f Avoid administration of other drugs known to prolong the QT interval (ie quinolones, macrolides, ondansetron), as well as various antiarrhythmic, antidepressant and antipsychotic drugs; Avoid administration of other drugs known to prolong the QT interval (ie quinolones, macrolides, ondansetron), as well as various antiarrhythmic, antidepressant and antipsychotic drugs;
- g A 12-lead ECG will be performed in a semi-supine position after resting for at least 5 minutes. The intention is to exclude the development of prolongation in the QT interval or bradycardia;
- h Blood samples will be collected to assess the COVID-19 infection and perform laboratory tests requested by the doctor. In the case of Manaus, the evaluation of the infection by COVID-19 will take place at LACEN-FVS and the others will take place at the Delphina Rinaldi Abdel Aziz Hospital and A & E. In Niterói-RJ all tests will be performed at the hospital. In Mato Grosso do Sul, the evaluation of infection by COVID-19 will take place at LACEN-MS and any others will take place at participating hospitals;

Version 2.0 23march2020

- i Blood samples will be collected for storage in a biorepository for further evaluation of the immune response profile;
- j Evaluated according to the DAIDS table for clinical and laboratory events;

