3. OBJECTIVES AND OUTCOMES

The general objective of the study is to evaluate the clinical efficacy, safety of therapy and reduction of mortality in hospitalized adult patients with severe respiratory syndrome using two different dosages of chloroquine. Objectives and outcomes are shown in table 2.

 Table 2: Objectives and outcomes.

| Objectives | Outcomes | | | | | | |
|--|---|--|--|--|--|--|--|
| Primary | | | | | | | |
| To assess whether the therapeutic regimen of | Reduction of mortality by 50% | | | | | | |
| Group 1 reduces mortality by 50% in the study | | | | | | | |
| population compared to Group 2. | | | | | | | |
| Secondary | | | | | | | |
| - Assess mortality on days 7, 14 and 28 after | - Mortality on days 7 and 14 | | | | | | |
| hospitalization; | - Clinical status of the subject on days 14 | | | | | | |
| - Assess clinical improvement (use of | and 28 | | | | | | |
| supplemental oxygen, ICU stay, length of stay | -Daily clinical status during | | | | | | |
| in the ICU, length of hospital stay, need for OTI | hospitalization | | | | | | |
| and time on mechanical ventilation, radiological | - Need for and duration of supplementary | | | | | | |
| alterations and time taken to improve the | oxygen | | | | | | |
| radiological and resonance pattern); | - Need for and duration of mechanical | | | | | | |
| - Assess the percentage of SARS-CoV2 | ventilation | | | | | | |
| detection in OPS and blood samples on days 1, | - Length of hospitalization | | | | | | |
| 3, 5, 7, 14 and 28 in the study population; | - Data and cause of death (if applicable) | | | | | | |
| Quantify the SARS-CoV2 virus in | - Prevalence of grade 3 and 4 adverse | | | | | | |
| oropharyngeal swab, nasal swab, OPS and blood | events; | | | | | | |
| samples on days 1, 3, 5, 7, 14 and 28 in the study | - Prevalence of serious adverse events; | | | | | | |
| population; | - Leukogram, hemoglobin, platelets, | | | | | | |
| - Alterations in white cell count, hemoglobin, | creatinine, CK, glucose, total bilirubin, | | | | | | |
| platelets, creatinine, glucose, total bilirubin, | ALT and AST on days 1, 3, 5, 7 (while | | | | | | |
| ALT and AST over time. | hospitalized); and on days 14 and 28 (if | | | | | | |
| - Cumulative incidence of serious adverse | patient is able to return to the clinic or is | | | | | | |
| events (SAEs); | still hospitalized); | | | | | | |
| - Cumulative incidence of grade 3 and 4 adverse | - Negative presence of the virus in | | | | | | |

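### Grade 3-4 and serious adverse event counts are not uniquely defined across the protocol, and the scheduled ECGs feed no listed outcome

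*Protocol*

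**What the plan says.** **Grading scale.** Section 9.2 takes its severity scale from "toxicity rating scales developed by the WHO and the National Institutes of Health, Division of Microbiology and Infectious Diseases", and says that it "will be used to rate the severity of all symptoms, physical examination findings and results of hemoglobin". The same section also bases safety on the "classification of laboratory assessments and vital signs", and sets a follow-up rule for "All laboratory abnormalities - with Grade 2 or greater for biological data". It names no scale for laboratory values other than haemoglobin. In Table 1 (section 1.12), footnote j to the adverse event row reads "Evaluated according to the DAIDS table for clinical and laboratory events".

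**Outcomes.** The synopsis list of secondary outcomes has "Incidence of serious adverse events (grades 3 and 4", with the grades in parentheses. The synopsis objectives likewise join grades 3 and 4 to seriousness in one item. Section 9.6 sets out the usual seriousness criteria (death, hospitalisation, disability and so on) but calls such an event a Severe AE. Table 2 in section 3 keeps grade 3-4 adverse events and serious adverse events on separate lines. Its objectives column speaks of cumulative incidence, while its outcomes column has "Prevalence of serious adverse events" and the same word for grade 3-4 events.

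**Recording.** Section 9.5 records physical or clinical symptoms as adverse events if they occur or worsen during the study and are judged related to the drug. Section 9.6 defines an adverse event as any unwanted medical occurrence, with no causal link needed.

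**ECG.** Table 1 marks a 12-lead ECG in every column. Footnote g gives the purpose: "The intention is to exclude the development of prolongation in the QT interval or bradycardia".

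**The concern.** A between-arm comparison of adverse events needs one rule for what is recorded, one scale for how it is graded and one definition of what is counted. Here each of the three has two versions, so two careful teams following the protocol could report different grade 3-4 and serious event counts from the same patients.

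The counts also carry much of the safety oversight. Section 8.1.2 states that there are no pre-specified stopping rules. Section 1.11.2 relies on a two-weekly blinded look at AE and SAE data, escalated if unexpected events are worrying in number. Section 7 links unmasking for the DSMB to SAEs.

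The ECG is a separate gap. Cardiovascular effects, arrhythmia and cardiac arrest among them, are the first item in the risk list of section 2.3.1.1. The tracings are planned and their purpose is stated, but nothing says how they enter the comparison of the two regimens.

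**Working it through.** The protocol states no safety rate or safety sample size, so there is no figure to reproduce. The check is a cross-reading.

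**1. Scale.** Table 2 lists nine laboratory measures as outcomes: white cells, haemoglobin, platelets, creatinine, CK, glucose, total bilirubin, ALT and AST. Section 9.2 names a scale for one of them, haemoglobin, which leaves 9 − 1 = 8 without a named scale there. Its Grade 2 follow-up rule nevertheless presupposes that laboratory values are graded. Footnote j gives clinical and laboratory events a DAIDS grade. For symptoms and haemoglobin two scales apply. For the other eight measures one section names a scale and the other does not.

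**2. What is counted.** The synopsis phrase can be read in three ways: the grades define seriousness; an event must be both serious and grade 3-4; or the parenthesis is a loose gloss and the 9.6 criteria govern. Three invented events show the effect:

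| Event | Synopsis: grade defines | Synopsis: both needed | Synopsis: 9.6 governs | Table 2, grade 3-4 line | Table 2, SAE line |
|---|---|---|---|---|---|
| Grade 3, no seriousness criterion met | in | out | out | in | out |
| Grade 2, prolongs hospital stay | out | out | in | out | in |
| Grade 3, prolongs hospital stay | in | in | in | in | in |

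On the first reading the synopsis outcome equals Table 2's grade 3-4 line. On the second it is the overlap of the two lines. On the third it is the SAE line. The use of Severe AE in 9.6 for seriousness criteria does not help a reader choose.

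**3. What is recorded.** A grade 3 symptom judged unrelated to the drug is an adverse event by the 9.6 definition but is not recorded under the symptom rule in 9.5. That rule applies before any grading or counting.

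**4. ECG.** The columns of Table 1 are D0 to D11 (12), Dx, D14 and D28: 12 + 3 = 15, all marked. The notes to the table stop all procedures at discharge, so the number of tracings varies by patient. The synopsis objectives, the synopsis outcomes and both columns of Table 2 contain no ECG or QT item. Section 9.2 names adverse events, laboratory assessments and vital signs as the basis for safety, not the ECG. The one remaining route is the general adverse event count: 9.6 is broad enough to admit a QT change, but the recording rule in 9.5 speaks of symptoms.

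**5. Context for the ECG.** By the dosing table in section 6.2, nominal totals are 600 mg × 2 × 10 = 12,000 mg in Group 1 and 450 mg × 2 + 450 mg × 4 = 2,700 mg in Group 2, a ratio of 12,000 / 2,700 = 4.4. This shows how far apart the exposures are. The protocol gives no relation between dose and QT, so it does not measure an error.

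**The case against.** The strongest reply is that these are inconsistencies in secondary outcomes, some perhaps from translation, and that summary measures and DSMB listings are normally left to an analysis plan or charter. That is fair for the choice of QTc summary. It does not reach the rest: the conflicts lie within the protocol, and an analysis plan cannot recover events or QTc values that were never entered.

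Four stronger readings are tempting, and the documents do not support them.

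- *Section 9.2 grades nothing but symptoms, physical findings and haemoglobin.* It also refers to classifying laboratory and vital-sign data and to Grade 2 laboratory abnormalities. What is missing is the named scale.
- *QT prolongation can never count.* Under 9.6 it can be entered as an adverse event, and adverse event incidence is a listed outcome. The route is weak but it exists. The missing ECG outcome also comes from the outcome lists, not from the scale conflict.
- *Prevalence lets abnormalities present at entry, such as shock, dilute the comparison.* Section 9.5 records symptoms only if they occur or worsen during the study, and the synopsis and Table 2's objectives column say incidence. The word is an inconsistency to correct. A dilution effect is not shown.
- *Fatal events are lost because only grades 3 and 4 are named.* Mortality is the primary outcome and cause of death is a listed secondary outcome.

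It is also fair to note that the cardiovascular risk item calls ECG changes rare, and that ECGs are not taken after discharge.

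**Conclusion.** The point holds in this limited form. Two grading scales are named, and 9.2 names none for most laboratory outcomes. Severity and seriousness are confused in the synopsis and in the terminology of 9.6 but separated in Table 2. Incidence and prevalence are both used. The causality condition in 9.5 contradicts the definition in 9.6. The grade 3-4 and SAE counts are therefore not uniquely defined. Separately, ECGs marked in 15 of 15 schedule columns feed none of the listed objectives or outcomes.

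The size in events cannot be given, since it depends on how many events are non-serious grade 3-4, serious at lower grades, judged unrelated, or seen only on ECG, and the protocol offers no rates for these. No direction of bias between arms is shown, because the same unclear rules apply to both under blinding. The primary mortality comparison is unaffected. The conclusion assumes that the protocol text governs data collection; a recording manual that already settles these points would reduce the practical effect but not the contradiction.

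**What to change.** Reconcile the synopsis objectives and outcomes, Table 1 footnote j, Table 2 and sections 9.2, 9.5 and 9.6 as follows.

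- Name one grading scale, covering clinical and laboratory events, and use it in both 9.2 and Table 1.
- List two separate incidence outcomes: (a) adverse events of grade 3 or higher that occur or worsen after D0; (b) serious adverse events by the 9.6 criteria, any grade. Replace prevalence with incidence and use the word serious in 9.6.
- Record both regardless of judged causality, and keep the relatedness judgement as a separate data item.
- Add (c), a by-arm summary of QTc from the ECGs already scheduled. Fix the measure in advance, for example change from D0 at set treatment days, and report the number of tracings per patient, because ECGs stop at discharge or death. A maximum over all tracings would depend on how many each patient has. Supply the summary to the DSMB.

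The cost is protocol wording, entry of QTc values from tracings already taken, and a small amount of analysis. No new procedure is needed, and no clinical threshold or management rule is proposed.
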